 # = eye drop
 a = Baseline and 15 min post-eye drop assessment
 b = 3-5 hour post-eye drop assessment
 c = 4 week post-eye drop assessment

*Visits 2b, 3b and 4b are scheduled 4 hours (± 30 mins) after the corresponding visits 2a, 3a and 4a on the same day, and therefore are not compulsory for all study participants to attend. Only those who are able to attend this visit will complete the assessment visits 2b, 3b and 4b.

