1. PROTOCOL SYNOPSIS

Table 1

Protocol Title	A two comparator, controlled phase 3 study of OM3 Tear formulation versus OPTIVE ADVANCED Unit Dose and OPTIVE Unit Dose eye drops in patients with and without evaporative dry eye.
Background	
 ○ The normal tear film is a relatively stable, thin film composed of a superficial lipid layer and an aqueous layer intermixed with a mucous gel layer, which is partially adherent to the corneal and conjunctival surface epithelium ○ Dysfunction of one or more components of the tear film can lead to loss of tear film stability and symptoms of dry eye ○ The majority of patients with dry eye are prescribed artificial tears to alleviate symptoms and maintain a healthy ocular surface ○ OM3 Tear is a new unit dose emulsion, containing flaxseed/castor oil, which is being developed by [REDACTED]. It is desirable to understand the effect that this new emulsion has on tear film evaporation and tear lipid profile via interferometry, in patients with evaporative dry eye (EDE) and those without (non-EDE). It would also be valuable to evaluate the retention time of the lipid components of the new emulsion via tear collection and analysis in EDE and non-EDE patients
Study Design	Single centre, double-masked, randomized, 3 arm comparison of OM3 Tear eye drops to two comparators.
Aims and Objectives	To measure tear film evaporation rate, tear lipid profile via interferometry and tear lipid components before and 15 mins, 1 hour and 4 hours after the first dose, and again after 4 weeks of use of the emulsion OM3 Tear eye drops, compared to two comparators (Optive Advanced Unit Dose and Optive Unit Dose).
Recruitment	September 2016
Study Start & End Dates	September 2016 – April 2017
Sample size	
Up to 40 participants will be recruited (approx. 20 EDE and 20 non-EDE subjects). This sample size was calculated on the basis of detecting a difference in:
 
 ○ tear evaporation rate between the eye drops of 36 gm⁻²/h where the expected standard deviation of the measurement is 50 gm⁻²/h, assuming an estimate of type 1 error $\alpha = 0.05$ and power of 80% for a two tailed test¹
Subject Source	UNSW and general community

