
Visit Schedule – 3 arm study
	
Visit 1 (Day -14): Screening visit, dispensing run-in product (Refresh Plus)
 
ARM 1:
 
Visit 2a (Day 1): Pre-instillation and 15 min (± 5 min) post-instillation assessment - Eye Drop #1
 
Visit 2b (Day 1): 1 hour (± 15 min) post-instillation assessment - Eye Drop #1
 
Visit 2c* (Day 1): 4 hour (± 30 min) post-instillation assessment - Eye Drop #1
 
Visit 3 (4 weeks): 4 week assessment - Eye Drop #1
 
ARM 2: (after minimum 2 week wash-out period using run-in product Refresh Plus)

	
Visit 4a ([6 weeks): Pre-instillation and 15 min (\pm 5 min) post-instillation assessment - Eye Drop #2
 
Visit 4b (6 weeks): 1 hour (\pm 15 min) post-instillation assessment - Eye Drop #2
 
Visit 4c* (6 weeks): 4 hour (\pm 30 min) post-instillation assessment - Eye Drop #2
 
Visit 5 (10 weeks): 4 week assessment - Eye Drop #2
 
ARM 3: (after minimum 2 week wash-out period using run-in product Refresh Plus)
 
Visit 6a (12 weeks): Pre-instillation and 15 min (\pm 5 min) post-instillation assessment - Eye Drop #3
 
Visit 6b (12 weeks): 1 hour (\pm 15 min) post-instillation assessment - Eye Drop #3
 
Visit 6c* (12 weeks): 4 hour (\pm 30 min) post-instillation assessment - Eye Drop #3
 
Visit 7 (16 weeks): 4 week assessment Eye Drop #3
 
Note: Subjects are NOT to instil any eye drops within 3 hours prior to the scheduled visits
 
* 4 hour assessments will only be conducted on participants who are able to attend this additional visit on the same day as the initial assessment

Procedure
	
Standard ocular examination and non-standard ocular examination procedures will be carried out at the scheduled visits.
 
Standard optometric procedures may include:
 
 ○ Subjective questionnaires (OSDI, Likert and VAS) ○ Corneal and conjunctival staining (Fluorescein and Lissamine Green) 
Non-standard optometric procedures may include:
 
 ○ Tear evaporation rate (Modified Vapometer, Delphin Technologies) ○ Tear Break-Up Time (with fluorescein) and lipid layer grade ○ Tear film lipid layer thickness (LipiView Interferometer) ○ [REDACTED] ○ [REDACTED] ○ [REDACTED]

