
Study Endpoints
	
The primary endpoint is a measurable difference in tear evaporation rate between the eye drops after initial application (15 min) and/or after 1 hour and/or 4 hours of application and/or after 4 weeks of daily use.
 
The secondary endpoints are (i) a measurable difference in TBUT between the

	
eye drops after initial application (15 min) and/or after 1 hour and/or 4 hours of application and/or after 4 weeks of daily use and (ii) a measurable difference in symptom improvement between the eye drops after initial application (15 min) and after 4 weeks of daily use.

Statistical Considerations
	
Paired t-tests, repeated measures ANOVA or linear mixed model analysis using Bonferroni adjustment for multiple comparisons and p value set at $p < 0.05$. Mann Whitney U test will be used to compare tear film lipidome between the eye drops.

IRB Status & Details
	
This clinical research study requires approval from the Human Research Ethics Committee at the University of New South Wales prior to study initiation, any advertising, and participant enrolment.
 
 ○ HREC meetings held monthly ○ Lead time for new applications: approx. 2 months

Dissemination of Results
	
 ○ Publication in peer-reviewed journals ○ Presentation at International conferences

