4. BACKGROUND INFORMATION

4.1. Background and Clinical Rationale

The normal tear film is a relatively stable, thin film composed of a superficial lipid layer and an aqueous layer intermixed with a mucous gel layer, which is partially adherent to the corneal and conjunctival surface epithelium. Dysfunction of one or more components of the tear film can lead to loss of tear film stability and symptoms of dry eye. The majority of patients with dry eye are prescribed artificial tears to alleviate symptoms and maintain a healthy ocular surface.

The purpose of this study is to evaluate the retention time of the lipid components of the new emulsion OM3 Tear eye drops via tear collection and analysis in evaporative dry eye (EDE) and non-EDE patients. Tear film evaporation rate, tear lipid profile via interferometry and tear lipid components will be evaluated before and 15 mins, 1 hour and 4 hours after the first dose, and again after 4 weeks of use of the emulsion OM3 Tear eye drops, compared to two comparators (Optive Advanced Unit Dose and Optive Unit Dose).

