5. STUDY OBJECTIVES AND CLINICAL HYPOTHESIS

5.1. *Study Objective*

The objective of this study is to measure tear film evaporation rate, tear lipid profile via interferometry and tear lipid components with the use of the emulsion OM3 Tear eye drops, compared to two comparators (Optive Advanced Unit Dose and Optive Unit Dose) in subjects with EDE and those without (non-EDE)

5.2. *Clinical Hypothesis*

Tear evaporation rate as measured with the Vapometer is better (i.e. lower) with the emulsion OM3 Tear formulation compared to at least one of the two comparators at one or more of the post eye drop instillation time-points.

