6. STUDY DESIGN

This study is a single centre, double-masked, randomized, 3-arm comparison of emulsion OM3 eye drops compared to two comparators. All study subjects will attend a Screening visit and receive REFRESH PLUS® for 2 weeks during a run-in period prior to randomization. Subjects will be randomized as to the order of allocation to use the OM3 Tear eye drop and the two comparators. For each arm of the study, assessments will be conducted prior to eye drop instillation and 15 min, 1 hour and 4 hours post-instillation. Subjects will then be dispensed with the randomized study eye drop and instructed to instill 1 to 2 drops of their assigned study product in each eye, as needed, but at least twice daily, for 4 weeks. Subjects will attend a 4 week visit assessment and then undergo a minimum 2 week wash-out period using run-in product REFRESH PLUS® before returning to complete the next arm of the study. These procedures will be repeated until the subjects have completed all 3 arms of the study.

The primary endpoint is a measurable difference in tear evaporation rate between the eye drops after initial application (15 min) and/or after 1 hour and/or 4 hours of application and/or after 4 weeks of daily use.

All proposed procedures conform to the NHMRC Statement on Human Experimentation.

Participants are considered enrolled when they have signed the informed consent form and are regarded as part of the clinical trial population.

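### The 1-hour assessment in the primary endpoint has no place in Table 4 or Table 5, the two schedules number visits differently, and Table 4 omits Screening TBUT

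*Combined protocol and SAP*

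**What the plan says.** **Where 1 hour is required.** The synopsis aims cover evaporation rate, "tear lipid profile via interferometry and tear lipid components before and 15 mins, 1 hour and 4 hours after the first dose". Section 4.1 repeats that these measures "will be evaluated before and 15 mins, 1 hour and 4 hours after the first dose". The synopsis schedule gives 1 hour its own label, "Visit 2b (Day 1): 1 hour", with a window of ±15 minutes, and repeats it as 4b and 6b for the second and third drops. The opening of Section 6 says that "assessments will be conducted prior to eye drop instillation and 15 min, 1 hour and 4 hours post-instillation". The primary endpoint (synopsis, Section 6 and Section 6.2) lists 15 minutes, 1 hour, 4 hours and 4 weeks, joined by and/or. The synopsis applies the same four times to a secondary endpoint, "a measurable difference in TBUT between the" eye drops.

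**What is optional.** In the synopsis, only the 4-hour visit: "4 hour assessments will only be conducted on participants who are able to attend this additional visit".

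**Where 1 hour is absent.** Table 4 (Section 6.1.1) has three columns per drop. Its key defines a as baseline and 15 minutes, c as 4 weeks, and "b = 3-5 hour post-eye drop assessment". The note to the table makes the b visits optional. Table 5 has the same three rows per drop, and the text of Section 6.1.4 allows at most three visits per drop.

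**Screening TBUT.** Table 4 marks fluorescein tear break-up time (TBUT) N, meaning not required, at Visit 1. The synopsis selection criteria and inclusion criterion 7 in Section 7.1.1 both require TBUT of 10 seconds or less in at least one eye at Screening.

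**The concern.** Section 6.1.1 makes Table 4 the statement of what is collected at each visit, so case report forms and bookings would naturally be built from it. A site that did so would not measure the 1-hour tear evaporation rate (TER), one of the four post-dose time points of the primary endpoint, for any drop. The 1-hour TBUT, interferometry and tear lipid components would go with it. None of these can be recovered afterwards.

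The gap falls where the schedule is already thin. Under the tables, the only same-day TER after 15 minutes comes from a visit that participants may skip. Anyone who skips it has no TER between about 20 minutes and 4 weeks. Section 4.1 gives the study's purpose as retention of the emulsion's lipid components, so the hours after instillation matter.

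The conflicting labels add a second risk. Sections 7.3.1 and 10.1 refer to visits by label, and those labels mean something else, or nothing, in the synopsis.

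**Working it through.** There is no stated figure to reproduce. The check compares the two schedules and counts.

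**Can an existing column hold the 1-hour reading?** The synopsis windows are 15 ± 5 min = 10–20 min for the first reading and 60 ± 15 min = 45–75 min for the 1-hour reading. Visit a covers baseline and 15 minutes, and visit b covers 3–5 hours. The interval 45–75 min lies outside both, so as labelled no column or row takes it. Table 4's headers, key and note agree with Table 5 and the text of 6.1.4, so this is not a broken table.

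**Labelled visits.**
- Synopsis: 1 + 3 × 4 = 13
- Tables 4 and 5: 1 + 3 × 3 = 10
- Difference: three 1-hour visits, one per drop

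**Post-dose TER points per participant.**

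| | Synopsis | Tables | Lost |
|---|---|---|---|
| All points | 3 × 4 = 12 | 3 × 3 = 9 | 3/12 = 25% |
| Excluding the optional 4-hour point | 3 × 3 = 9 | 3 × 2 = 6 | 3/9 = 33% |
| Non-optional, same day, after 15 min | 3 × 1 = 3 | 0 | 3/3 |

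**Maximum across the trial.** 3 × 40 = 120 TER assessments. Four measures are due at 1 hour (TER, TBUT, interferometry, tear lipid components), so the maximum over all four is 4 × 120 = 480.

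**Labels used in both schedules.**

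| Label | Synopsis | Tables 4 and 5 |
|---|---|---|
| 1 | Screening | Screening |
| 2a | Day 1, drop 1, baseline and 15 min | same |
| 2b | Day 1, drop 1, 1 h | Day 1, drop 1, 3–5 h |
| 2c | Day 1, drop 1, 4 h | Week 4, drop 1 |
| 4a | Week 6, drop 2, baseline and 15 min | Week 12, drop 3, baseline and 15 min |
| 4b | Week 6, drop 2, 1 h | Week 12, drop 3, 3–5 h |
| 4c | Week 6, drop 2, 4 h | Week 16, drop 3 |

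Five of the seven differ. Table 4's timeline row (day or week, and drop number) exposes four of the five. It does not separate 2b, which is Day 1 with drop 1 in both.

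Section 10.1 dispenses run-in product at Visits 1, 2c and 3c, and Section 7.3.1 takes 4c as the 4-week visit. Both follow the table numbering. In the synopsis numbering, 2c and 4c are optional 4-hour visits and 3c does not exist.

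**Smaller conflicts found alongside.** Visit b is 3–5 hours in the Table 4 key and in Table 5, but 4 hours ± 30 minutes after visit a in the note to Table 4; the synopsis times it from instillation. The synopsis applies the TBUT criterion at Screening and Baseline, Section 7.1.1 at Screening only. Section 7.3.1 points to Table 5 for assessments that are listed in Table 4.

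**The case against.** The missing 1-hour label is not in dispute. The case on the other side concerns how much it matters.

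- **The endpoint survives.** It is joined by and/or, and the hypothesis in Section 5.2 asks only for benefit "at one or more of the post eye drop instillation time-points". This stands: the trial can still test its hypothesis without 1 hour. It does not tell the site whether to make a measurement that Section 6 says will be made.
- **One hour may be part of the initial attendance.** The synopsis calls only the 4-hour assessment an additional visit, so baseline, 15 minutes and 1 hour could be one stay, and three visits per drop could then be right. This stands in part: 13 against 10 counts labelled visits, not necessarily trips to the clinic. But the synopsis labels 1 hour separately and visit a does not include it, so the reading has no home in the tables either way.
- **The totals are worst cases.** True. They assume full recruitment, full completion and a site that uses only the tables. This is one centre, and the text of Sections 6 and 6.2 does mention 1 hour.
- **The numbering is editorial.** Largely fair. The body of the protocol is consistent with itself, the synopsis is the odd one out, and the timeline row clears up four of the five labels.
- **Screening TBUT is still implied.** Fair. Table 4 marks the eligibility check Y at Visit 1, and criterion 7 needs TBUT there. The N is still wrong.
- **A new 1-hour column meets the each-visit wording in Sections 11.2 and 12.2** (history, acuity, slit lamp). True but small: Table 4 already departs from it by omitting biomicroscopy at the b visits.

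**Conclusion.** The concern holds as stated and should be fixed before data collection. The plan requires a 1-hour assessment in its aims, background, design text and primary endpoint, and leaves it out of the table that tells the site what to collect. If the tables are followed, each participant loses 25% of possible post-dose TER points, or 33% of the non-optional ones, and keeps no non-optional same-day point after 15 minutes. The ceiling is 120 TER assessments, assuming all 40 participants complete three drops. The hypothesis remains testable; what is lost is one of its four time points and most of the assured same-day time course. The label conflict and the Screening TBUT entry are real but secondary.

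**What to change.** Reconcile the synopsis schedule, Table 4 and its key, Section 6.1.4 with Table 5, and the visit labels in Sections 7.3.1 and 10.1 to one visit list with one numbering. Then do one of the following:

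- **If 1 hour is intended**, as the aims, endpoint and design text indicate: add a 1-hour column per drop to Table 4 with TER, TBUT, LipiView and tear collection marked Y. Add 1-hour rows to Table 5, and bring the visit count in 6.1.4 into line. State whether 1 hour is a separate visit or part of the initial one, and which of the each-visit procedures in Sections 11.2 and 12.2 apply.
- **If it is not intended**: remove it from the aims, background, synopsis schedule, endpoints and design text.

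In either case mark TBUT Y at Visit 1. While editing, state one window and one reference time for the 4-hour visit, settle whether the TBUT criterion also applies at Baseline, and point Section 7.3.1 to Table 4.

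The cost is edits to two tables, a key, some cross-references and the case report form labels. A site that has planned from the tables would also need a 1-hour assessment of four measures on three days per participant. The synopsis and Section 6 already specify that, so the stated design does not grow.

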6.1.2. Randomisation and Masking

Prior to initiation of study treatment, each subject who provides informed consent will be assigned to a subject number that will serve as the subject identification number on all study documents. Subject numbers will be assigned in ascending order and should not be omitted or reused.

At the Screening visit (Visit 1), all eligible subjects will receive run-in product (REFRESH PLUS) for use during the 14-day run-in period. The clinical site will dispense the run-in product. At the time of randomization (Visit 2, Arm 1), eligible subjects will be randomly assigned to 1 of the 3 treatments. A randomization scheme will be prepared in advance.

Study product will be labeled with study product kit numbers. At Visit 2 (Arm 1), the specific study product kit number for each randomized subject will be dispensed by unmasked administrative study personnel and all study measurements will be conducted by the masked investigator. Unused study product will be returned at the 4 week follow-up visit and the run-in product will be dispensed to be used during the wash-out period. This procedure will be repeated until all arms of the study have been completed.

The emulsion OM3 Tear formulation and the two comparator unit dose eye drops will be provided in similar 0.4 mL unit-dose vials (comparator products will have commercial labeling).

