6.1.3. Clinical Trial Population

40 participants (approx. 20 EDE and 20 non-EDE subjects) will be recruited for the study.

Trial participants will be recruited from the local population at the investigational site. [REDACTED]

[REDACTED]

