13.1.1. Number of Participants

Up to 40 participants will be recruited (approx. 20 EDE and 20 non-EDE subjects). This sample size was calculated on the basis of detecting a difference in: tear evaporation rate between the eye drops of 36 gm²/h where the expected standard deviation of the measurement is 50 gm²/h, assuming an estimate of type 1 error $\alpha = 0.05$ and power of 80% for a two tailed test.

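### Section 6.1.2 does not say which drop orders are used or whether they are balanced, and no planned comparison names a period effect, so drift over 16 weeks would cost precision

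*Combined protocol and SAP*

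**What the plan says.** Section 6 (Study Design) describes a crossover: "Subjects will be randomized as to the order of allocation to use the OM3 Tear eye drop and the two comparators". Participants complete all three periods, and between periods they "undergo a minimum 2 week wash-out period using run-in product". An assessment before instillation opens each period.

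Section 6.1.2 (Randomisation and Masking) governs the allocation list. It says that at Visit 2 "eligible subjects will be randomly assigned to 1 of the 3 treatments", that "A randomization scheme will be prepared in advance", and, after describing dispensing, that "This procedure will be repeated until all arms of the study have been completed". It gives no set of orders, ratio, blocking or stratification factor.

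Section 6.1.3 states that "40 participants (approx. 20 EDE and 20 non-EDE subjects) will be recruited for the study", and the objective in Section 5.1 covers both groups. Section 13.1.1 bases the sample size on a difference in "tear evaporation rate between the eye drops of 36" g/m²/h with an SD of 50.

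For analysis, the synopsis offers paired t-tests, repeated measures ANOVA or a linear mixed model. Section 13.1.3 lists paired and group t-tests, Wilcoxon tests, repeated measures ANOVA and Friedman's test. Neither names a period, sequence or carry-over term.

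**The concern.** In a crossover the drop comparison is made within a person but across time. If evaporation rate drifts between periods, a participant's difference between two drops contains that drift, with a sign and size set by the order in which the drops were used. Using each participant as their own control does not remove it. Balanced orders cancel it on average, and a period term takes it out of the residual. The plan commits to neither.

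Drift is plausible: on the synopsis schedule each participant is followed from Day 1 to week 16, within a study running from September to April. The documents give no figure for its size.

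The choice of orders also matters for carry-over. Someone building the list from Section 6.1.2 could randomise the first drop only and let the rest follow in a fixed cycle.

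**Working it through.** **1. The plan's own figure.** Inputs from Section 13.1.1: difference 36, SD 50, two-sided α 0.05, power 80%. Treat 50 as the SD of the paired difference; the plan does not say whether it is. The normal approximation gives n = (50 × (1.960 + 0.842) / 36)² = 15.1, so 16. The exact paired t calculation gives 18 (power 82%), and 20 gives 86%. So about 20 per group is consistent with a paired calculation done within each group. A parallel reading with about 13 per arm (40/3) would have only 45% power, so the sample size supports the crossover reading.

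**2. Order imbalance under simple randomisation** (an assumption, since no scheme is given). Over the six orders, two given drops are one period apart in four orders and two periods apart in two. The mean squared period difference is (4 × 1² + 2 × 2²) / 6 = 2. The SD of the mean period difference is therefore √(2/n):
- n = 20: √0.100 = 0.32 (0.31 to 0.32 in simulation)
- n = 40: √0.050 = 0.22

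**3. The same with blocks of six.** Complete blocks contribute zero. With n = 20 there are three blocks and two further participants, drawn without replacement from the six orders. The variance of their sum is 2 × 2 × (6 − 2)/(6 − 1) = 3.2, so the SD is √3.2 / 20 = 0.09. The largest possible value is (2 + 1)/20 = 0.15.

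**4. Effect on power.** Let drift be d g/m²/h per period (assumed; linear). Under simple randomisation the unadjusted paired difference has SD √(50² + 2d²). Power for 36 uses the noncentral t with parameter 36√n / SD. It is for one pair of drops at one time-point, before any Bonferroni correction.

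| d | SD of paired difference | Unadjusted, n = 20 | Unadjusted, n = 40 |
|---|---|---|---|
| 0 | 50.0 | 86% | 99% |
| 10 | 52.0 | 84% | 99% |
| 20 | 57.4 | 76% | 97% |
| 36 | 71.4 | 57% | 87% |

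In simulation at n = 20 with participant, drop and period in the model, power stays at about 86% for every d under simple randomisation, and about 88% with blocks of six.

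**5. Bias or noise?** In simulation under simple randomisation, the type I error of the unadjusted paired test stays near 5% at every d, because the drift also widens the spread of the paired differences and so the standard error.

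**6. What balance adds.** Blocking without a period term leaves the unadjusted test at d = 20 with power of about 78–79% and type I error of about 3%, because the drift is still in the residual. With period modelled, simple randomisation inflates the variance of a drop contrast by 5.6% on average (95th percentile 17%), against 0.4% with blocks of six. The period term does most of the work.

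**7. Cyclic orders.** With only ABC, BCA and CAB in equal numbers, periods balance. But A, when it follows another drop, always follows C; B always follows A; and C always follows B. Carry-over could not then be separated from the drop effect.

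**The case against.** Several points on the other side stand.

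- A reader might infer that the two sections conflict over whether this is a crossover or a parallel trial. They do not: the sentence in Section 6.1.2 is tied to Visit 2, Arm 1, and reads naturally as the first-period assignment. The synopsis schedule and Sections 6 and 6.1.4 make the three-period crossover plain.
- A reader might infer that no balancing is planned. The documents are silent, which is different. The scheme prepared in advance may well be blocked, and block details are often kept out of a protocol to protect concealment.
- A reader might infer that the drop comparisons are biased. Under genuine randomisation of order they are not (step 5).
- The imbalance of simple randomisation and the fixed predecessor of a cyclic scheme are alternatives and cannot both apply. Neither scheme is stated. The wash-out of at least two weeks on a common product and the pre-instillation readings reduce the carry-over concern, although the documents offer no data that two weeks is enough and plan no check.
- A linear mixed model is among the options and could carry a period term.

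What remains is that the orders are not named, and that every listed comparison can be run as written without period.

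**Conclusion.** The point holds as a gap in specification with a cost in precision. If drift is small, the cost is negligible: at 10 g/m²/h per period, power with 20 participants falls from 86% to 84%. It becomes material in the groups of 20 at about 20 per period (76%) and serious at 36 (57%). With all 40 participants, power stays at 97% or more up to 20 per period.

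These figures assume linear drift, simple randomisation to six orders, and 50 as the SD of the paired difference. The drift values are assumptions; 20 per period means 40 across the three periods, more than the effect sought, so it is towards the high end. The change is still worth making before the list is generated, because the orders cannot be rebalanced afterwards and the remedy costs little.

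**What to change.** **Section 6.1.2.** Replace the assignment sentence with wording such as: *At Visit 2a participants are randomised to one of the six possible orders of the three eye drops. Orders are balanced by permuted blocks, with block details held in a separate restricted document.* Where EDE class can be determined from the pre-instillation evaporation rate before dispensing, add stratification by EDE group.

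**Section 13.1.3.** Name one primary comparison of evaporation rate: a linear mixed model with participant, drop and period. Add drop-by-EDE-group if group-specific effects are to be reported; an EDE main effect alone leaves within-person drop contrasts unchanged.

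**Cost.** The list and the analysis model both change; no participants are added. Stratifying needs two more things. The cut-off of 110 in Section 7.1.1, still marked as unconfirmed, must be fixed. The rate must also be calculated before the first kit is issued, from three readings per eye under open and closed conditions plus the surface area from the Screening photograph (Section 11.2), with the Schirmer rule applied to discordant eyes. If that cannot be done at the visit, balance overall and a period term still secure most of the gain.

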10. TREATMENT OF PARTICIPANTS

10.1. Administration of Study Eye Drops

The study eye drops will be dispensed to each randomized subject at Visits 2a, 3a and 4a. Run-in product will be dispensed at Visits 1, 2c and 3c. Each subject will be instructed by the investigator to instill 1 to 2 drops in each eye, as needed, but at least 2 times daily. The same vial can be used for both eyes, and should be used one time only. The vial should be discarded after each usage. If the subject is concurrently using approved Restasis or glaucoma therapy drops during the study and run-in period, they should be instructed to wait a minimum of 15 minutes between drop instillations. Subjects should be instructed not to instill any eye drops within 3 hours prior to their scheduled study visits.

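### Called double-masked, but Section 6.1.2 masks only the investigator and leaves the comparators commercially labelled, so participant masking of the self-reported symptom endpoint is not delivered as written

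*Combined protocol and SAP*

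**What the plan says.** The design claim appears twice. The synopsis (Study Design) reads "Single centre, double-masked, randomized, 3 arm comparison of OM3 Tear eye drops to two comparators", and Section 6 reads "This study is a single centre, double-masked, randomized, 3-arm comparison".

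Section 6.1.2 (Randomisation and Masking) is the only supplied text on how this is achieved:

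- Unmasked administrative staff dispense the kit, and "all study measurements will be conducted by the masked investigator".
- On labels: "Study product will be labeled with study product kit numbers".
- On containers: OM3 Tear and the two comparators "will be provided in similar 0.4 mL unit-dose vials". A parenthesis in the same sentence adds that "comparator products will have commercial labeling".
- Unused product comes back at the 4-week visit. The text does not say who receives it.

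Sections 6, 10.1 and 10.4 set home use: on demand, with a minimum of two instillations a day for 4 weeks per product, from a vial discarded after each use. Every participant receives all three products in randomised order.

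Synopsis secondary endpoint (ii) is symptom improvement at 15 minutes and at 4 weeks. Section 6.3 lists subjective comfort scores. Sections 9.1 and 11.2 collect both on paper questionnaires. Section 10.2.2 makes the optometrist responsible for documenting dispensing on the case record form and in the tracking spreadsheet.

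**The concern.** A double-masked trial normally masks the participant as well as the assessor. Here the masking section covers the assessor, does not mention the participant, and states that two of the three products carry commercial labeling. A site could hand participants visibly branded vials without departing from anything in 6.1.2.

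This matters most where the participant is the assessor. A participant who can tell a marketed brand from the new product may score symptoms partly on expectation. In this within-subject design the same person rates all three products, so such an expectation would enter the product comparison directly. A symptom difference could then not be presented as a double-masked result.

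**Working it through.** The plan gives no figure on masking to reproduce. The check sets the provisions side by side and counts what they reach.

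**1. Who is masked.**

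| Role | Section | Status |
|---|---|---|
| Investigator taking measurements | 6.1.2 | Masked |
| Administrative staff dispensing kits | 6.1.2 | Unmasked |
| Optometrist documenting dispensing | 10.2.2 | Not stated |
| Person receiving returned product | 6.1.2 | Not stated |
| Participant | Synopsis, 6 | Implied only by the term double-masked |

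**2. Whether anything described hides the brand from the participant.** There are three candidates.

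- Kit numbers: the text does not say whether the number is on the vial, pouch or carton, or whether it covers the brand.
- Similar vials: similar shape and volume do not conceal a printed brand, and the same sentence says the comparators are commercially labelled.
- Separate dispensing staff: this shields the investigator, not the person who receives the kit.

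No supplied text describes over-labelling, label removal or opaque packaging.

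**3. Handling.** 4 weeks × 7 days = 28 days. At a minimum of two instillations a day and at least one vial each, 28 × 2 = 56 vials per product. Over the two comparators, 2 × 56 = 112. These are nominal minimums.

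**4. Outcomes reached.** Endpoint (ii) has 2 time points × 3 products = 6 symptom assessments per participant.

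- The 3 at 4 weeks follow the home use in step 3.
- The 3 at 15 minutes follow the first dose in clinic. Section 6 puts dispensing after the same-day assessments ("Subjects will then be dispensed with the randomized study eye drop"). Section 10.1 says "The study eye drops will be dispensed to each randomized subject at Visits 2a, 3a and 4a". By the key to Table 4, those visits hold both the baseline and the 15-minute assessment, so both sections allow dispensing after the 15-minute scores. Exposure then turns on who opens and instils the first vial and whether the participant sees it, and neither section says.

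Section 5.2 compares OM3 with each comparator. Both of those contrasts (2 of 2) set OM3 against a commercially labelled product. This is a count of reach, not of bias.

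**5. The primary endpoint.** Tear evaporation rate is a Vapometer reading taken by an investigator stated to be masked, so the self-report route does not apply. Two routes remain.

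- Dosing is on demand above the minimum, so product knowledge could change how much is used before the 4-week reading.
- Section 6.1.2 gives dispensing to unmasked administrative staff, while 10.2.2 has the optometrist document it. If that optometrist also takes the measurements, assessor masking depends on what the record shows. The documents do not settle this.

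**The case against.** The strongest reply is that this is an omission in the text and not a demonstrated unmasking. The trial is declared double-masked twice. The kit-number sentence is general and not confined to OM3, and making the vials similar would have less purpose if only the investigator were masked. The commercial labeling may be on an outer carton that participants never receive. Consent pages and some other text are absent from the supplied copy, and Section 11.2 is redacted just after the comfort questionnaire is introduced, so detail on what participants know could lie there.

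Part of this stands. A reader might infer that participants do see the brand, and the documents do not show that. The location of the commercial labeling and the coverage of the kit label are both unstated.

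It does not remove the point. Section 6.1.2 appears complete. Its one explicit statement about the comparators' appearance runs against participant masking, and nothing stated there offsets it.

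A second tempting inference is that the different dispensing descriptions in Sections 6 and 10.1 expose the 15-minute scores. They do not, because both allow dispensing after that assessment.

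It is also fair to say that only a secondary endpoint is directly at risk. That limits the weight of the point. It does not justify treating the primary endpoint as fully protected.

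**Conclusion.** The point holds: as written, the described procedures do not deliver the participant masking that the synopsis and Section 6 claim. The confidence attaches to what the text provides, not to what participants actually see.

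It bears mainly on the self-reported symptom and comfort endpoint, which is one of the two synopsis secondary endpoints, and above all on the 3 assessments at 4 weeks. The 3 at 15 minutes are undetermined. The documents give no basis for the size or direction of any bias, and a reader should not assume that it favours OM3.

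Two opposite readings of the primary endpoint should be resisted. The documents do not show it to be biased, since it is an instrument reading. Nor do they show it to be fully protected, given on-demand dosing and the unreconciled account of who handles and records dispensed product.

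The conclusion assumes that the text missing from the supplied copy contains no concealment procedure. A sponsor who has one should state it in 6.1.2. The change should be made, but the point does not call the whole trial into question.

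**What to change.** 1. In 6.1.2, replace the commercial-labeling provision with concealment of the brand on all three products, on any packaging the participant handles, including the first-dose vial. An identical kit-number over-label is one way. Because the vials are only similar, describe any visible difference that remains. State who opens and instils the first dose.
2. If that is not done, change double-masked to investigator-masked in the synopsis and Section 6, and report and interpret the symptom endpoint as participant-unmasked.
3. In either case, reconcile 6.1.2 with 10.2.2 so that whoever takes the measurements neither handles nor records the identity of dispensed or returned product.

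Cost: concealment adds a small materials and handling cost that the documents do not allow to be priced. The alternative is two wording edits, a statement in 6.1.2 and a qualifier on the symptom results. Either may need an amendment reviewed by the sponsor and the ethics committee under 15.1.3, since a change to masking is not clearly administrative or logistical. Neither adds visits, measurements or participants.
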